Regular doses on days except for the visits will be administered no later than 9:00 AM, regardless of the specified dosing timing (i.e., before or after breakfast). The study drug should be administered at the almost same time every day throughout the study (acceptable range is ± 3 hours) except the visit day. The investigator or subinvestigator will confirm whether the subject has taken the study drug or not in the morning of each visit.

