9.1.5 Vital Sign Procedure

Vital signs will include office sitting blood pressure (systolic and diastolic), office standing blood pressure (systolic and diastolic), office sitting pulse rate, and office standing pulse rate (pulse rate per 1 minute). All office blood pressure will be measured with a blood pressure meter specified by the sponsor.

Office blood pressure should be measured at the time of trough (approximately 21 to 27 hours after the latest dose, i.e., in the morning of that day) with the subject without taking the study drug in the morning of the scheduled visit except for Week 16. The subject, the subject's parent, or legal guardian will be instructed strongly not to take the study drug at home on the scheduled visit day except for Week 16. The subject, the subject's parent, or the subject's legal guardian will be instructed again if the subject receives the study drug before the measurements of vital signs on the scheduled visit day by mistake.

When vital signs are scheduled at the same time as blood draws, vital signs will be obtained before the scheduled blood draw.

Office sitting blood pressure after taking the study drug will be also measured only at Week 16 of the Treatment Period; the time point which the pharmacokinetics after receiving the study drug is evaluated.

Subjects will be instructed not to eat or bathe within 1 hour before office blood pressure measurement, not to intake any caffeine containing product 30 minutes before the measurement.

<Determining difference in blood pressure between right and left arm>

At screening, sitting blood pressure in the right and left arms will be measured once after sitting at rest for ≥ 5 minutes to determine the difference in blood pressure between the arms. The arm with a higher systolic blood pressure will be used to measure office blood pressure during the study.

The right arm will be used if systolic blood pressure is the same on both sides. Change of the arm for measurement will not be allowed during the study.

<Measuring sitting blood pressure and sitting pulse rate>

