9.2 Monitoring Subject Treatment Compliance

Compliance with study drug (amount of dispense and return) between the visits, timing of the study dose (before or after breakfast) and the latest dosing date and time before collecting sample for pharmacokinetic evaluation will be confirmed and recorded in the eCRF.

Subjects, the subjects' parent, or the subjects' legal guardian will be instructed to be compliant with the study drug throughout the study. If a subject is noncompliant (< 70% or > 130%) with the study medication (TAK-536 placebo) during the Run-in Period, the subject will be excluded before the start of the Treatment Period, as indicated in the exclusion criteria No. 5. If a subject is noncompliant with the study medication (TAK-536) (eg, failure to take < 50% of the scheduled doses after the last visit) after the start of the Treatment Period, it may be appropriate to withdraw the subject from the study. All subjects should be reinstructed about the dosing requirement during study contacts. The authorized study personnel conducting the re-education must document the process in the subject source records.

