5.0 ANALYSIS ENDPOINTS

Primary Efficacy Endpoint

<Safety>

AEs, anthropometric (weight, height, and body mass index [BMI]) measurements, laboratory tests, resting 12-lead electrocardiogram (ECG), and vital signs (office standing blood pressure, office sitting pulse rate, office standing pulse rate, and home sitting blood pressure)

Secondary Efficacy Endpoints

<Efficacy>

Office trough* sitting diastolic and systolic blood pressures

* Trough: The time point immediately before the next dosing, when the blood drug concentration is assumed to be lowest

Proportion of subjects who achieve the target blood pressure**

** Target blood pressure: < 95th percentile shown in Table 5.a Reference Blood Pressure Values of Children by Gender and Age for essential hypertension, < 90th percentile shown in Table 5.a Reference Blood Pressure Values of Children by Gender and Age for secondary hypertension

Table 5.a Reference Blood Pressure Values of Children by Gender and Age

					•	O
		Boy			Girl	
	90th	95th	99th	90th	95th	99th
6 years old	110/70	114/74	121/82	108/70	111/74	119/81
7 years old	111/72	115/76	122/84	109/71	113/75	120/82
8 years old	112/73	116/78	123/86	111/72	115/76	122/83
9 years old	114/75	118/79	125/87	113/73	117/77	124/84
10 years old	115/75	119/80	127/88	115/74	119/78	126/86
11 years old	117/76	121/80	129/88	117/75	121/79	128/87
12 years old	120/76	123/81	131/89	119/76	123/80	130/88
13 years old	122/77	126/81	133/89	121/77	124/81	132/89
14 years old	125/78	128/82	136/90	122/78	126/82	133/90
15 years old	127/79	131/83	138/91	123/79	127/83	134/91
16 years old	130/80	134/84	141/92	124/80	128/84	135/91

Systolic/diastolic blood pressures (mmHg, JCS2012)

The 90th, 95th, and 99th indicate 90th, 95th, and 99th percentiles, respectively.

<Pharmacokinetics>

Plasma concentrations of TAK-536 and its metabolites (M-I and M-II)

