7.0 METHODS OF ANALYSIS AND PRESENTATION

7.1 General Principles

7.1.1 Study Definitions

- Day of last observation/test or contact, whichever comes later: Last date of SDTM.SV
- Treatment-emergent adverse event (TEAE): Any AE occurring after the first study drug administration for the Treatment Period
- Pretreatment event (PTE): Any AE occurring after obtaining informed consent but before the first study drug administration for the Run-in Period
- Adverse event during the Run-in Period: For subjects who enter the Treatment Period, any
 AE occurring after the first study drug administration for the Run-in Period until the first
 study drug administration for the Treatment Period. For subjects who do not enter the
 Treatment Period, any AE occurring after the first study drug administration for the Run-in
 Period
- Summary statistics: Number of subjects, mean, standard deviation, maximum, minimum, and quartiles
- Duration of exposure to study drug for the Treatment Period: Date of the last study drug administration for the Treatment Period – Date of the first study drug administration for the Treatment Period + 1
- Study period after the study drug administration for the Treatment Period: Date of last observation/test or contact – Date of the first study drug administration for the Treatment Period + 1
- Compliance rate with the study drug for the Treatment Period: Total number of doses of study drug for the Treatment Period (Amount of study drug dispensed for the Treatment Period Amount of study drug returned for the Treatment Period) / Duration of exposure to study drug for the Treatment Period × 100 (rounded to 1 decimal place)
- Office trough sitting diastolic and systolic blood pressures on each measuring day: The mean of 3 values on a given measuring day (rounded to integers) is used as the representative value of that measuring day.

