- Achievement of target blood pressure on each measuring day: Subjects are determined to have achieved their target blood pressures if their blood pressures are the < 95th percentile (both diastolic and systolic) shown in Table 5.a Reference Blood Pressure Values of Children by Gender and Age for essential hypertension or < 90th percentile (both diastolic and systolic) shown in Table 5.a Reference Blood Pressure Values of Children by Gender and Age for secondary hypertension. If either systolic or diastolic blood pressure is missing, it will be handled as missing data. The age at the time of informed consent will be used.

- Disease duration (years): (Date of informed consent [year and month] Time of onset [or diagnosis] of underlying disease [year and month]) / 12 (rounded to 1 decimal place) For the date of informed consent, only the year and month will be used. If the year of onset (or diagnosis) of underlying disease is unknown, it will be classified as "Unknown." If only the month of onset (or diagnosis) of underlying disease is unknown, the disease duration will be calculated with the month of onset (or diagnosis) of underlying disease as January.
- QTcF interval: Fridericia's formula (QT interval / [RR interval^{0.33}])
- CV (%): Standard deviation / mean × 100

7.1.2 **Definition of Study Days**

- Study Day: The day before the first study drug administration for the Treatment Period will be defined as Day -1 and the day of the first study drug administration for the Treatment Period will be defined as Day 1.
- Follow-up Day: The day after the last study drug administration for the Treatment Period will be defined as Follow-up Day 1.

7.1.3 **Definition of Study Visit Windows**

For each test, observation, and endpoint except for home blood pressure, all evaluable data (i.e., non-missing data) will be handled according to the following rules.

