For each visit other than the End of Treatment Period I and the End of Treatment Period, the evaluable data within the acceptable time window will be used. If more than one evaluable datum lies within the same acceptable time window, the data whose test/observation/evaluation time point is closest to the scheduled time point will be used. If there are two data equidistant to the scheduled time point, the data obtained later will be used. The temporal distance from the scheduled time point will be determined based on the Study Day and the time interval between the latest study drug administration and the blood sample collection.

For the End of Treatment Period I and the End of the Treatment Period, the evaluable data within the acceptable time window with the largest Study Day will be used.

Table 7.a Visit Window of Office Sitting Blood Pressure and Pulse Rate

Visit	Cahadulad Study Day	Acceptable Time Window	
Visit	Scheduled Study Day	Study Day	Follow-up Day
At the End of Run-in Period (Week 0)	Study Day: 1	-28 to 1	
Week 2	Study Day: 15	2 to 22	< 4
Week 4	Study Day: 29	23 to 43	< 4
Week 8	Study Day: 57	44 to 71	< 4
Week 12	Study Day: 85	72 to 99	< 4
Week 16 (postdose)	Study Day: 113	100 to 127	< 4
Week 20	Study Day: 141	128 to 155	< 4
Week 24	Study Day: 169	156 to 183	< 4
Week 32	Study Day: 225	184 to 253	< 4
Week 40	Study Day: 281	254 to 323	< 4
Week 52	Study Day: 365	324 to 372	< 4
Week 54 (Follow-up Period)	Study Day: 379	373 to 386	> 0
At the End of Treatment Period I*1		2 to 99	< 4
At the End of Treatment Period*2		2 ≤	< 4

^{*1} Data obtained after the earliest day of addition or dose change of antihypertensive drugs other than RAS inhibitors during the Treatment Period will not be used for summaries. Not applicable for office sitting pulse rate.
*2 The condition of *1 will not apply to this handling. Not applicable for office sitting pulse rate.

Table 7.b Visit Window of Clinical Laboratory Test Items

Visit	Scheduled Study Day	Acceptable Time Window	
V ISIL	Scheduled Study Day	Study Day	Follow-up Day
At the End of Run-in Period (Week 0)	Study Day: 1	-28 to 1	
Week 2	Study Day: 15	2 to 22	< 15
Week 4	Study Day: 29	23 to 43	< 15
Week 8	Study Day: 57	44 to 71	< 15
Week 12	Study Day: 85	72 to 99	< 15
Week 16 (postdose)	Study Day: 113	100 to 141	< 15
Week 24	Study Day: 169	142 to 225	< 15
Week 40	Study Day: 281	226 to 323	< 15
Week 52	Study Day: 365	324 to 379	< 15

Table 7.c Visit Window of Office Standing Blood Pressure and Pulse Rate

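### Office blood pressure is analysed as trough without any check on time since dose, so readings known to be post-dose enter the on-treatment trough and end-of-period results

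*SAP*

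**What the plan says.** Protocol 9.1.5 fixes the timing at every visit except Week 16: "Office blood pressure should be measured at the time of trough (approximately 21 to 27 hours after the latest dose". The same section foresees a dose taken before the measurement. Its stated response is that the child or guardian "will be instructed again if the subject receives the study drug before the measurements of vital signs on the scheduled visit day by mistake". Under Protocol 8.1.3 the investigator or subinvestigator "will confirm whether the subject has taken the study drug or not in the morning of each visit".

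SAP 5.0 defines the endpoint in words: "Trough: The time point immediately before the next dosing, when the blood drug concentration is assumed to be lowest". The derivation in SAP 7.1.1 is "The mean of 3 values on a given measuring day (rounded to integers) is used as the representative value of that measuring day". Under SAP 7.1.3, "all evaluable data (i.e., non-missing data) will be handled according to the following rules", and for ordinary visits "the evaluable data within the acceptable time window will be used". Table 7.a gives that window for office blood pressure in Study Days and Follow-up Days only. For End of Treatment Period I and End of Treatment Period, the evaluable reading with the largest Study Day is taken.

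On dosing times, Protocol 9.2 says that "the latest dosing date and time before collecting sample for pharmacokinetic evaluation will be confirmed and recorded in the eCRF".

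**The concern.** Trough pressure was chosen partly to show that the effect persists over the dosing interval (Protocol 6.2). A reading taken soon after a dose would be expected to overstate that effect, and one taken well beyond 27 hours to understate it. If both can sit in the trough rows unmarked, the mean change and the proportion at target mix different quantities, and the planned tables cannot show how many values were true troughs.

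The SAP does treat timing as important for plasma samples. Table 7.g sorts them into 21-27 hours (predose) and 1-3 hours (postdose). No such rule exists for blood pressure, although Protocol 9.1.5 has vital signs taken just before the blood draw at the same visit.

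**Working it through.** **1. Following the rule for one child.** Suppose a child doses at home by mistake and attends Week 12 two hours later.
- Plasma sample: Table 7.g places 2 hours in the 1-3 hour postdose class, so it stays out of the predose row.
- Blood pressure: the reading is non-missing and inside Study Days 72-99, so it enters the Week 12 trough mean, the change from Week 0 and the target proportion. If it is the last reading up to Day 99, it is also the End of Treatment Period I value.
- SAP 7.8.2 says that visits other than Week 16 are measured before dosing. That describes intended conduct and gives no rule for a reading that departs from it. SAP 7.8.4.2 excludes only missing results.

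**2. Week 16 and the end-of-period rows.** Week 16 is post-dose by design (Protocol 8.1.3, 1-3 hours), with a window of Days 100-127. End of Treatment Period I stops at Day 99, so its window does not reach Week 16. End of Treatment Period accepts any Study Day from 2 onward, takes the latest, and does not exclude Week 16. A child with no later eligible reading contributes the post-dose value.

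**3. Readings after the last dose.** Follow-up Day 1 is the day after the last dose (SAP 7.1.2), and on-treatment rows accept Follow-up Day < 4. Nominal hours = 24 × Follow-up Day, ±3:

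| Follow-up Day | Hours since last dose | Within 21-27 h |
|---|---|---|
| 1 | 21-27 | yes |
| 2 | 45-51 | no |
| 3 | 69-75 | no |

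For illustration, with the 12.8-hour adult half-life (Protocol 6.2) and mono-exponential decline, plasma level relative to 24 hours is 2^(−24/12.8) = 0.27 at 48 hours and 2^(−48/12.8) = 0.07 at 72 hours. These are concentrations, not blood pressure effects.

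**4. Size of the post-dose bias.** The documents give no mistiming rate. Assume 4-10% of 50 readings (2 to 5 children) are post-dose and lie 3-8 mmHg below trough. Bias in the mean change = fraction × difference:
- low: 0.04 × 3 = 0.12 mmHg
- high: 0.10 × 8 = 0.80 mmHg

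The standard errors implied by SAP 6.0 are 10.5/√50 = 1.48 mmHg (diastolic) and 15.5/√50 = 2.19 mmHg (systolic). The high case is thus 0.54 and 0.36 of a standard error. One reading moves the target proportion by at most 1/50 = 2 percentage points, and only if it crosses the threshold.

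**5. Does the stated power survive a restriction?** Exact one-sample t-test, two-sided 0.05, changes and SDs from SAP 6.0:

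| Usable readings | Diastolic | Systolic |
|---|---|---|
| 50 | 99.0% | 98.9% |
| 45 | 98.2% | 98.0% |
| 40 | 96.8% | 96.6% |
| 30 | 90.6% | 90.0% |
| 29 | 89.6% | 89.0% |

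The plan's figure of at least 90% is reproduced at 50, and it holds down to 30 timed readings.

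**The case against.** Several points on the other side stand.

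- **Scope.** A reader might infer that every visit except Week 16 is affected. At Week 0 the child has taken only placebo, and Week 54 is off drug by design. Neither can be a mistimed on-treatment trough.
- **The Follow-up Day limit.** A reader might call the acceptance of readings up to 72 hours after the last dose an error. It matches Protocol 9.3.5, which allows office pressure within 3 days of early termination, counting the day after the final dose as day one. It looks deliberate, and Follow-up Day 1 is a valid trough.
- **Checkability.** A reader might infer that timing at Weeks 20-52 cannot be verified at all. The documents do not support that. The morning dose is asked about at each visit, and deviations are documented, with significant ones entered in the eCRF (Protocol 14.2). What can be said is that the dosing time is tied to pharmacokinetic sampling, and SAP Table 7.f ends at Week 16. The eCRF and the schedule appendix are not visible.
- **Substitution.** Dropping a Week 12 reading does not make End of Treatment Period I missing. An earlier reading, normally Week 8, replaces it. Week 8 is a titration visit, and Protocol 6.2 sets 4 weeks at the highest dose, so exclusion alone can trade a timing error for a titration-stage error.
- **Unseen rules.** Protocol 13.1.1 and 13.1.3 place data-handling detail in a Handling Rule for Analysis, and SAP 7.3.7.2 cites a Subject Evaluability List. A timing rule could sit in either. That lowers confidence, but the SAP's own definition of evaluable as non-missing would then contradict it.

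These points narrow the concern and shape the remedy. They do not supply the missing rule.

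**Conclusion.** The point holds for Weeks 2-12, Weeks 20-52 and the two end-of-period rows. Applied as written, the SAP counts readings known to be post-dose as trough, and it lets a planned post-dose Week 16 value stand as End of Treatment Period. Readings on Follow-up Days 2 and 3 are a legitimate allowance that should be kept and counted.

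The change should be made, but the stakes are modest. The endpoint is secondary, the t-test is for reference only, and the bias is 0.12-0.80 mmHg under the assumed 4-10% and 3-8 mmHg, against planned changes of −6.5 and −9.5 mmHg. Late readings pull the other way. It would go too far to infer that the efficacy result is invalid or the sample size inadequate: the stated power is met and would survive restriction to 30 timed readings. Confidence is medium, because the Handling Rule for Analysis is not available.

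**What to change.** In SAP 7.1.3 and Table 7.a:

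1. Do not use the Week 16 post-dose reading for End of Treatment Period.
2. At Weeks 2-12 and 20-52, do not count as trough a reading known to follow a dose that morning, whether from the confirmation in Protocol 8.1.3 or from the dosing time recorded at pharmacokinetic visits. Leave Week 0 and Week 54 exempt.
3. Keep Follow-up Day 2 and 3 readings. Report per visit how many readings fall outside 21-27 hours and how many have unknown timing.
4. Show the End of Treatment Period I change and target proportion twice, with all readings and with 21-27 hour readings only, stating how many children had an earlier visit substituted.

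If the eCRF does not already capture it, record the date and time of the last dose at Weeks 20-52. If the Handling Rule for Analysis already holds a timing rule, cite it and align the definition of evaluable.

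The cost is some SAP wording, the added counts, one repeat table and possibly one eCRF field. A few readings leave the trough rows. For End of Treatment Period I an earlier, possibly pre-titration, reading may stand in, which is why both versions are shown.

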9.3.5 Final Visit or Early Termination

The Final Visit will be performed on Week 52 or at the Early Termination Visit.

The tests and observations specified for each visit will be performed.

For subjects early terminate the study after the start of the Treatment Period, if possible, the same tests, observations, and evaluations as those scheduled at Week 52 should be performed.

Whenever possible, office sitting blood pressure should be determined within 3 days after early termination and the other tests, observations, and evaluations should be performed within 14 days after early termination (the next day of the final dose should be calculated as the first day).

For all subjects who entered the Treatment Period, the investigator or subinvestigator must complete the Subject Status on eCRF page with the first day when the subjects received the study drug for the Treatment Period and study completion or early termination status until Week 24 and study completion status at Week 52 for subjects who continuingly received the study drug beyond Week 24.

9.3.6 Follow-up Period: Week 54

Follow-up Period will begin the first day after the final administration of TAK-536 for the Treatment Period and will continue until 2 weeks. The tests and observations specified for each visit will be performed. If subjects terminate the study drug in the Run-in Period or at an early stage of the Treatment Period, no tests, observations, and evaluations will be required but care should be taken for subject safety.

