13.1.3 Efficacy Analysis

(1) Secondary endpoints and analytical methods

[Secondary endpoints]

Office trough sitting systolic and diastolic blood pressure, proportion of subjects who achieve the target blood pressure

[Analytical methods]

The analyses discussed below will be conducted with the FAS.

Summary statistics (number of subjects, mean, standard deviation, maximum, minimum, and quartiles; hereinafter the same) and 2-sided 95% confidence intervals for mean values will be calculated for the office trough sitting systolic and diastolic blood pressure at each time point (including the end of the Treatment Period I and the end of the Treatment Period II; hereinafter the same).

Summary statistics and 2-sided 95% confidence intervals for mean values will be calculated referring to a 1-sample t-test for the change of office trough sitting systolic and diastolic blood pressure from the end of the Run-in Period (Week 0) to each time point during the Treatment Period.

The proportion of subjects who achieve the target blood pressure at each time point during the Treatment Period will be summarized.

(2) Data conversion methods and handling of missing data

Details of data conversion methods and handling of missing data will be defined in the Handling Rule for Analysis and SAP.

(3) Significant level and confidence coefficient

Significant level: 5% (2-sided test)

Confidence coefficient: 95% (2-sided estimates)

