13.1.5 Safety Analysis

[Primary endpoints]

AEs, anthropometric (weight, height and BMI) measurements, laboratory tests, resting 12-lead ECG, and vital signs (office standing blood pressure, office sitting pulse rate, office standing pulse rate, and home sitting blood pressure)

[Analytical methods]

The following analyses will be conducted with the safety analysis set.

1) AEs (Treatment-emergent AEs)

A treatment-emergent AE (TEAE) is defined as any AE occurring after the start of TAK-536 administration of the Treatment Period.

The incidence of TEAEs listed below will be analyzed. TEAEs will be coded using the Medical Dictionary for Regulatory Activities (MedDRA). The frequency distribution will be provided using the system organ class (SOC) and preferred term (PT) using MedDRA as follows:

- TEAEs
 - Drug-related TEAEs
 - Severity of TEAEs
 - Severity of drug-related TEAEs
 - TEAEs leading to study drug discontinuation
 - Serious TEAEs
 - TEAEs over time
- 2) Anthropometric (weight, height and BMI) measurements, laboratory tests, resting 12-lead ECG, and vital signs (office standing blood pressure, office sitting pulse rate, office standing pulse rate, and home sitting blood pressure)

For continuous variables, the observed values and the changes from the end of the Run-in Period (Week 0) will be summarized for each time point. In addition, individual figures of the observed values will be provided.

For categorical values, shift tables of the data before and after administration will be provided.

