7.11.3 Vital Signs and Weight

Analysis set:

Safety analysis set

Analysis variable(s):

Office sitting pulse rate

Office standing systolic blood pressure, Office standing diastolic blood pressure, Office standing pulse rate

Home sitting systolic and diastolic blood pressures

Height, Weight

Visit

Office sitting pulse rate: Weeks 0, 2, 4, 8, 12, 16 (postdose), 20, 24, 32, 40, 52, 54 (Follow-up Period)

Office standing blood pressure and pulse rate: Weeks 0, 12, 24, and 52

Home blood pressure: Week 0 (predose), Week 0 (postdose), Weeks 2, 4, 8, and 12

Height and weight: Weeks 0, 12, 24, 40, and 52

Analytical method(s):

The following analysis will be performed for the above analysis variables by weight group (\leq 50 kg, \geq 50 kg) and in the combined weight groups.

The measurement of office sitting pulse rate at Week 16 will be performed after the study drug administration, while the measurement at other visits than Week 16 will be performed before the study drug administration.

(1) Summary statistics for observed values and changes (each visit after administration [each visit other than Week 0] – Week 0) will be provided for each visit.

Home blood pressure will be provided for changes (each visit after administration [each visit other than Week 0 (predose)] – Week 0 [predose]).

- (2) Case Plots
- (3) Overall frequency distributions of home blood pressure during the Treatment Period. See "9.0 APPENDIX" for the criteria."

7.11.4 **12-Lead ECGs**

Analysis set:

Safety analysis set

Analysis variable(s):

Heart rate

RR interval

PR interval

QT interval

QTcF interval

QRS interval

Resting 12-lead ECG interpretation [Within normal limits, Abnormal but not clinically significant, Abnormal and clinically significant]

Visit:

Weeks 0, 12, 24, and 52

Analytical method(s):

The following analyses (1) and (2) will be performed for the above analysis variables excluding resting 12-lead ECG interpretation by weight group ($< 50 \text{ kg}, \ge 50 \text{ kg}$) and in the combined weight groups.

The following analysis (3) will be performed for resting 12-lead ECG interpretation by weight group ($< 50 \text{ kg}, \ge 50 \text{ kg}$) and in the combined weight groups.

- (1) Summary statistics for observed values and changes (each visit after administration [Week 12 to Week 52] Week 0) will be provided for each visit.
- (2) Case Plots
- (3) Shift tables at Week 0 and each visit after administration

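### Most primary safety variables have no end-of-treatment row, so an early-termination value that shares a visit window usually drops out of the by-visit and shift tables

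*SAP*

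**What the plan says.** SAP 7.1.3 sets the selection rule for every test except home blood pressure. For ordinary visits, "If more than one evaluable datum lies within the same acceptable time window, the data whose test/observation/evaluation time point is closest to the scheduled" day is the one kept, and "If there are two data equidistant to the scheduled time point, the data obtained later will be used". A different rule serves the end-of-period rows: "the evaluable data within the acceptable time window with the largest Study Day will be used".

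Those rows are printed only in Table 7.a (office sitting blood pressure and pulse). Home blood pressure has a separate end-of-Period-I rule. Both Table 7.a footnotes add "Not applicable for office sitting pulse rate", and the sitting pulse visit list in SAP 7.11.3 has no end-of-period visit. Tables 7.b (laboratory), 7.c (standing blood pressure and pulse), 7.d (height and weight) and 7.e (ECG) have no such row. Nor do the visit lists in 7.11.2.1, 7.11.2.2, 7.11.3 and 7.11.4; for example, "Office standing blood pressure and pulse rate: Weeks 0, 12, 24, and 52".

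Protocol 9.3.5 asks that children who stop early have the Week 52 assessments if possible. It gives sitting blood pressure a 3-day limit, while "the other tests, observations, and evaluations should be performed within 14 days after early termination".

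Protocol 13.1.3 has efficacy values summarised "at each time point (including the end of the Treatment Period I and the end of the Treatment Period II; hereinafter the same". Protocol 13.1.5 then says of the continuous safety variables that "the observed values and the changes from the end of the Run-in Period (Week 0) will be summarized for each time point". SAP 7.13 declares one change from the protocol, the added efficacy use of home blood pressure.

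**The concern.** Safety is the primary objective, and these variables are primary endpoints. The plan secures each child's last value for sitting blood pressure, a secondary endpoint, but not for laboratory tests, ECG, standing blood pressure, pulse or growth.

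The windows are wide. A child who attends a scheduled visit and then stops may have the termination assessment in the same window. The closest-to-schedule rule then usually keeps the scheduled value. The assessment nearest to the decision to stop is collected but appears in no by-visit summary or shift table for that variable.

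**Working it through.** The plan states no figure on this point, so there is none to reproduce. The check applies the SAP 7.1.3 rule to the windows in Tables 7.a to 7.e.

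**Rule.** Let N be the scheduled day, s the day of the scheduled assessment and e a later termination day in the same window. The termination value is left out if |e − N| > |s − N|. It is kept if it is closer or tied.

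**Examples**
- ECG on Day 169, termination ECG on Day 200. Both lie in the Week 24 window (128 to 267). |200 − 169| = 31 > 0, so Day 200 is left out.
- Laboratory tests on the same two days share the Week 24 window (142 to 225), with the same result.
- Sitting pulse on Day 200 falls in the Week 32 window (184 to 253). With no other value there, it is kept under the Week 32 label.
- Laboratory tests on Day 275, six days before the Week 40 day (281). Termination on Day 287 ties at 6 days and replaces the scheduled value. Termination on Day 288 (7 days) is left out.

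**Count with on-time visits (s = N).** Every termination day after N, up to the window's upper edge, is left out:
- Laboratory: (22−15)+(43−29)+(71−57)+(99−85)+(141−113)+(225−169)+(323−281) = 7+14+14+14+28+56+42 = 175
- Sitting pulse: (22−15)+(43−29)+(71−57)+(99−85)+(127−113)+(155−141)+(183−169)+(253−225)+(323−281) = 7+6×14+28+42 = 161
- Standing blood pressure and pulse; ECG: (127−85)+(267−169) = 42+98 = 140
- Height and weight: (127−85)+(225−169)+(323−281) = 42+56+42 = 140

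Termination from Day 2 to Day 364 gives 363 possible days. The last column starts on the day after the first scheduled post-baseline assessment (Day 15 or Day 85).

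| Variable | Days left out | Share of Days 2–364 | Share after first assessment |
|---|---|---|---|
| Laboratory | 175 | 175/363 = 48% | 175/349 = 50% |
| Sitting pulse | 161 | 161/363 = 44% | 161/349 = 46% |
| Standing BP and pulse | 140 | 140/363 = 39% | 140/279 = 50% |
| ECG | 140 | 140/363 = 39% | 140/279 = 50% |
| Height and weight | 140 | 140/363 = 39% | 140/279 = 50% |

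**Sensitivity to visit timing.** Assume scheduled visits deviate uniformly by up to 3, 7 or 13 days, and weight equally every pair of visit day and later termination day in one window. The termination value is left out in this share of pairs:

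| Variable | ±3 days | ±7 days | ±13 days |
|---|---|---|---|
| Laboratory | 93% | 85% | 76% |
| Sitting pulse | 90% | 80% | 65% |
| Standing BP, ECG | 98% | 95% | 90% |
| Height and weight | 96% | 92% | 86% |

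**Standing blood pressure timing.** Table 7.c accepts Follow-up Days below 4. Protocol 9.3.5, read literally, allows this test up to Day 14. A reading on Follow-up Days 4 to 14 keeps to the protocol limit but cannot enter the Table 7.c summaries, whatever the window overlap.

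**The case against.** A reader might infer that termination values are always lost when windows are shared, or that the safety signal disappears. The documents support neither.

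- The rule keeps a termination value that is closer or tied, which happens after an early scheduled visit. A value alone in its window is also kept.
- The MAV table (SAP 7.11.2.1 and 9.2) uses every evaluable value up to 14 days after the last dose for 11 chemistry items, including potassium, creatinine, eGFR, ALT and AST.
- Under protocol 10.1.2, clinically significant laboratory and ECG changes are adverse events, reported under the diagnosis where there is one. The adverse event tables use no one-value-per-visit rule. A child who stops because of an event appears there.
- Case plots are planned for the continuous variables. The SAP does not say whether they use windowed or all values.
- A by-visit table is meant to show the value nearest the visit. In the example the child stays in the Week 24 row with the Day 169 value, so that row is not wrong, and no bias in it has been shown.
- These values need not be on-treatment. The protocol cites a half-life of 12.8 hours in healthy adults; five half-lives are 64 hours, about 2.7 days, against a limit of 14 days.
- The parenthesis in protocol 13.1.3 stands in the efficacy section, and the synopsis states the safety summaries without it. Carrying it into 13.1.5 is an inference.
- The Table 7.a pulse footnote may mean only that the condition on antihypertensive changes does not apply to pulse. The 7.11.3 visit list is the firmer evidence.
- Protocol 9.1.5 has standing blood pressure follow sitting blood pressure, so in practice both may fall within 3 days. Protocol 9.3.5 does not say so.

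All of this narrows the point. What remains is that haematology, urinalysis, ECG, standing blood pressure, pulse and growth have no MAV backstop, and none of these variables has a last-value summary.

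**Conclusion.** The point holds as a gap in the summaries, not as a loss of all safety information. An early-termination value that shares a window with a scheduled value is left out of the by-visit summaries and shift tables unless it is at least as close to the scheduled day.

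The size is 39% to 48% of possible termination days from Day 2 to Day 364, depending on the variable. It assumes on-time visits and a termination assessment within the table's Follow-up Day limit. Reading a percentage as a share of children also needs stopping times spread evenly. It would be too strong to say that about half of all early terminators are affected for every variable. A figure near 50% holds for laboratory tests, ECG, standing blood pressure, and height and weight only when days before the first scheduled post-baseline assessment are excluded.

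The plan gives no expected number of early terminators, so the number of children cannot be estimated. Each is 2% of the planned 50.

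Protocol 13.1.3 and 13.1.5 together suggest that end-of-period safety summaries were intended, but do not establish it. The case for change rests on completeness of the primary safety tables at small cost.

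**What to change.** 1. Add an End of Treatment Period row to SAP Tables 7.b to 7.e, and state in Table 7.a that the row applies to sitting pulse. Use the rule already applied to sitting blood pressure: largest Study Day from Day 2, within each table's existing Follow-up Day limit.
2. Add that visit to the summaries, and to the shift tables where planned, in SAP 7.11.2.1, 7.11.2.2, 7.11.3 and 7.11.4.
3. Footnote the row for laboratory tests, ECG, and height and weight: it may include values taken up to 14 days after the last dose.
4. Separately, reconcile protocol 9.3.5 with SAP Table 7.c, so that standing blood pressure and pulse collected within the protocol limit can be analysed.

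The cost is one more row per table, a footnote and a short wording change for item 4. No visit or procedure is added. The downside is that the new row mixes values taken on the drug with some taken after it, which is why the footnote is needed.
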